Title:

Pain perception with cervical tenaculum placement during office procedures: A randomized controlled trial

Authors:

[name]; [name] MS, [name]

ClinicalTrials.gov

NCT ID: NCT02969421

Protocol Date:

December 22, 2016

Introduction

Gynecology is undergoing a transformation in the location of care delivery. As a result of technological innovations, procedures are migrating from the hospital and ambulatory surgical center to the office setting. There are numerous advantages to office-based procedures. They include reduced patient expenses, improved scheduling convenience, favorable provider reimbursement, enhanced continuity of care, and patient satisfaction.¹ However, success of office-based procedures is based on numerous factors such as patient selection, physician competency, teamwork and communication, along with adequate and safe anesthesia.²

The goal of most office-based procedures is twofold: (1) to be able to safely and successfully perform the procedure, and (2) patient comfort. The experience of pain is influenced not only by physical factors but also by psychological and social factors. Regardless of procedure type, anxiety, depression, and a woman's anticipation of the pain she will experience are strong predictors of the pain experienced during office gynecologic procedures. For procedures that involve cervical dilation and passage of a device or cannula through the internal os of the cervix, a history of dysmenorrhea, nulliparity, and postmenopausal status are associated with increased pain.³

The importance of patient counseling and patient selection remains pivotal in success of in-office procedures.⁴ Numerous studies have focused on optimal pain control during in-office procedures analyzing analgesia, anesthesia, anxiolytics, combination regimens, local anesthesia, and nonpharmacologic techniques. The indisputable evidence thus far supports the idea that a multimodal approach may be most effective in achieving adequate pain control.^{3,4} However, what steps can we take with our procedural methods to further improve patient comfort.

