The two commonly described strategies for tenaculum placement, slow versus having the patient cough while the tenaculum is placed are utilized by providers based on preference and/or their previous training. There is no published study that compares these methods to one another. Doty and Goldthwaite utilized each method separately. In Doty's study that compared tenaculum type, patients were asked to cough at time of vulsellum or single-tooth tenaculum placement, no local or systemic analgesic was used, and pain was measured using a 100-mm visual analog scale.⁵ In Goldthwaite's study that compared lidocaine injection versus jelly, the tenaculum was closed slowly over 3 seconds and pain was rated using a 100-mm visual analog scale.⁶ Our study aims to compare these strategies, slow tenaculum placement versus the cough method, and their effects on pain at time of placement. Provider satisfaction with tenaculum placement will be measured as a secondary outcome. Overall pain with IUD insertion will also be a secondary outcome. I hypothesize that slow tenaculum placement is less painful to patients and offers higher provider satisfaction scores.

Methods and Materials

Randomized controlled trial from December 2016 to April 2017 at Duke University Medical Center Gynecology Clinics.

Data to be collected from each subject prior to randomization:

- Age
- Parity
- Race
- Highest education level achieved
- Number of cesareans
- BMI
- History of chronic pain
- Daily narcotic use
- GAD7 Score

Inclusion criteria:

- Women ages 18 years and older
- Undergoing IUD placement
- English or Spanish speaking

Exclusion criteria:

- Primary language other than English or Spanish

Sample size determination

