Visual analog scale (VAS) is a continuous scale comprised of a horizontal or vertical line, usually 10 centimeters (100 mm) in length, anchored by 2 verbal descriptors, one for each symptom extreme. For pain intensity, the scale is most commonly anchored by “no pain” (score of 0) and “worst imaginable pain” (score of 100). The respondent is asked to place a line perpendicular to the VAS line at the point that represents their pain intensity. Using a ruler, the score is determined by measuring the distance (mm) on the 10-cm line between the “no pain” anchor and the patient’s mark, providing a range of scores from 0-100. The following cut points on the pain VAS have been recommended: no pain (0-4 mm), mild pain (5-44 mm), moderate pain (45-74 mm), and severe pain (75-100 mm).⁷ Todd et.al in their quest to address the question of clinical significance of VAS scores, found that 13 mm is the minimum mean change on a standard 100-mm visual analog pain scale that should be considered clinically significant for acute, traumatic pain.⁸ This finding was later validated in a prospective, observational cohort study by Gallagher et.al.⁹

We have chosen a 16 mm difference on a standard 100-mm visual analog pain scale as value of clinical significant. In order to detect at least a 16 mm difference with 90% power and alpha of .05, we estimated a total sample size of 66.

Randomization:

All patients meeting study criteria will be randomized using computer generated random numbers (randomization.com). This is not a blinded study so patients and providers will be aware of the group each subject is randomized to. This randomization will be revealed prior to speculum placement.

Procedure at time of IUD insertion:

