A single-tooth tenaculum will be used in placement of all IUDs. Each subject will be placed in the standard dorsal lithotomy position. To start data collection, each subject will be asked to rate their baseline pain. After speculum placement, and adequate visualization of the cervix by the provider, the subject will be asked to rate their pain using a 100-mm visual analog scale. The provider will then place the tenaculum on the anterior lip of the cervix closing to the first ratcheted click over a 5 second period. At this point, the subject will be asked to rate their pain using a 100-mm visual analog scale. If the subject was randomized to the cough arm, the subject will be asked to give one strong cough. This first cough will serve as a test cough. If provider is pleased by the strength of the patient’s cough, the subject will then be asked to cough again and at this cough the tenaculum will be placed on the anterior lip of the cervix. Only one test cough will be allowed. At this point, the subject will be asked to rate their pain using a 100-mm visual analog scale. All subjects will be asked to rate their overall pain at the completion of the procedure. The provider will be asked to rate their satisfaction with tenaculum placement on a Likert-type 5 point satisfaction scale. 1: not at all satisfied, 2: slightly satisfied, 3: moderately satisfied, 4: very satisfied, 5: extremely satisfied.

A script will be read by the provider during the process of IUD insertion. The script reads as follows.

Provider Says: First, we will place each foot in its footrest. Please lay back and slide your bottom downward towards me. I will tell you when to stop. On your scoring sheet, please mark your pain at this time.

Provider does: Place speculum and achieve adequate visualization of the cervix.

[figure not shown]
Provider says: On your scoring sheet, please mark your pain at this time.

Provider does: Clean cervix. Place tenaculum on anterior lip of cervix in accordance to your randomized group.

[figure not shown]
Slow Method

The tenaculum is to be placed on the anterior lip of the cervix.

After visualization of the anterior lip of the cervix, open the tenaculum and close it slowly over 5 seconds to the first ratcheted click. No more than 1 cm of cervix should be grasped between your tenaculum teeth.

Maximum amount of cervix to grasp

Too much cervix grasped

Cough Method

The tenaculum is to be placed on the anterior lip of the cervix.

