Costs to the Subject –Participation will not result in any costs to subjects.

Data collection:

REDCap, web-based password-protected relational database will be created prior to study initiation. All patients consented for the study will have a REDCap generated subject ID code. This code will be used for subject identification. The REDCap database will also store the following information from each subject ID; age, parity, race, level of education, the patient's pain responses, and provider satisfaction.

Statistical analyses:

We will compare groups on the primary outcome of pain using T-tests versus Wilcoxon test pending the normality of the results. We will compare groups on the secondary outcome of provider satisfactions with placement using Chi-square test or Fisher's exact test. We will evaluate for potential correlations based on patient demographics and physician experience.

Privacy, Data Storage & Confidentiality – All paper data will be kept secured in a locked cabinet in [name] office. The data will be retained until the conclusion of the data analysis, then destroyed per IRB guidelines. Only the PI and the personnel listed will have access to the paper data.

During data collection, subject identifiers and relevant data elements will be recorded in the RedCap database. Then, study-specific identification numbers will be assigned to each subject. Prior to dissemination of any information in this database beyond the DUMC's secure servers or firewall, all identifiers will be stripped from the database and data will only be referenced by the study-specific identification numbers. Deidentified data exported from RedCap will be stored in an excel spreadsheet, on a secure network folder managed by the department of Obstetrics and Gynecology in on a secure server behind the Duke University Medical Center firewall. Only study staff listed as key personnel with the IRB will have access to the study folder. The name of the secure network folder will be the same as the IRB protocol number.

A master log, which links the study-specific identification number to the study subject, will be generated. The master log will be stored on the same secure network server mentioned in the above paragraph.

Any publications or presentations that result from this research will not identify any subjects individually, and will present data in aggregate form only.

References

-

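### The primary test is chosen by the normality of the outcome data, no effect estimate in mm is named, and the baseline pain score enters no stated analysis

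*Combined protocol and SAP*

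**What the plan says.** The Statistical analyses section has three sentences. The one on the primary outcome reads: "We will compare groups on the primary outcome of pain using T-tests versus Wilcoxon test pending the normality of the results". It names no normality test, threshold or default, and no mean difference, Hodges-Lehmann shift or confidence interval. The second sentence covers provider satisfaction. The third promises correlations with demographics and physician experience, which is not an adjusted treatment comparison.

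The other relevant places are these.

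- **Introduction, last paragraph.** The aim is to compare "slow tenaculum placement versus the cough method, and their effects on pain at time of placement". Overall pain with IUD insertion is secondary.
- **Sample size determination.** "In order to detect at least a 16 mm difference with 90% power and alpha of .05, we estimated a total sample size of 66". The same section cites 13 mm as the smallest clinically significant mean change for acute traumatic pain. It gives no SD.
- **Procedure at time of IUD insertion.** "To start data collection, each subject will be asked to rate their baseline pain". Further scores follow after the speculum, at tenaculum placement and at completion.
- **Randomization.** "This randomization will be revealed prior to speculum placement". The study is unblinded.

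**The concern.** The trial is justified by a difference in mm, so its main result should be an estimate in mm with an interval that can be read against 16 mm and 13 mm. As written, both the test and any estimate reported with it can be settled after the outcome data are seen, in an unblinded study.

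A t-test goes naturally with a mean difference. A Wilcoxon test can be reported with a Hodges-Lehmann shift, also in mm, but the two are the same quantity only if the effect is a pure shift. The plan names neither.

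A baseline score is also collected from everyone and then left out. If it predicts placement pain, adjusting for it would narrow the interval at no extra burden to subjects.

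**Working it through.** **Inputs.** From the documents: 16 mm, 13 mm, total 66, power 90%, alpha 0.05. Assumed because the documents do not say: two-sided test, 33 per arm, no dropout, SD 20 mm, baseline-outcome correlation r.

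**The plan's own figure.** The 66 cannot be reproduced from stated inputs because no SD is given. With SD 20 mm, n per arm = 2 × (1.960 + 1.282)² × 20² / 16² = 32.8, so 33 per arm and 66 in total. Solving the exact t-test for 90% power at 33 per arm gives SD 19.75 mm. A one-sided test with SD 22 mm would also give 66.

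**Adjustment, normal theory.** Residual SD = 20 × √(1 − r²); SE = residual SD × √(2/33); noncentral t with noncentrality δ/SE, on 64 df unadjusted and 63 df with one covariate. Unadjusted, SE = 20 × 0.2462 = 4.92 mm and 16/4.92 = 3.25.

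| Analysis | Residual SD (mm) | SE (mm) | Power at 16 mm | Power at 13 mm |
|---|---|---|---|---|
| Unadjusted | 20.0 | 4.92 | 89.3% | 73.9% |
| Adjusted, r = 0 | 20.0 | 4.92 | 89.2% | 73.9% |
| Adjusted, r = 0.2 | 19.6 | 4.82 | 90.4% | 75.6% |
| Adjusted, r = 0.3 | 19.1 | 4.70 | 91.8% | 77.8% |
| Adjusted, r = 0.5 | 17.3 | 4.26 | 95.9% | 85.1% |

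The 95% CI half-width, taken as 1.96 × SE, goes from 9.65 mm unadjusted to 8.36 mm at r = 0.5.

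**Simulation against the data-driven switch.** There were 5,000 runs per case. Outcomes were beta-distributed on 0 to 100 with SD 20. Baseline was floored, with mean 5 and SD 8, and scores were rounded to 1 mm. The plan gives no switching criterion, so one was assumed: Shapiro-Wilk p < 0.05 in either arm leads to Wilcoxon, otherwise Welch t. Latent r of 0, 0.2, 0.3 and 0.5 corresponds to an observed Pearson r of about 0, 0.16, 0.24 and 0.42, so these columns do not line up exactly with the table above. Entries are power (%), regression with HC2 standard error v switch.

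| Arm means (skew) | r = 0 | r = 0.2 | r = 0.3 | r = 0.5 |
|---|---|---|---|---|
| 40 v 56 (mild) | 88.0 v 88.4 | 89.2 v 88.7 | 89.8 v 88.3 | 93.4 v 88.4 |
| 30 v 46 (moderate) | 88.4 v 89.6 | 89.5 v 89.5 | 89.4 v 88.7 | 93.1 v 89.5 |
| 20 v 36 (strong) | 88.2 v 94.2 | 88.5 v 93.6 | 89.8 v 93.7 | 93.4 v 94.3 |
| 40 v 53 (mild) | 72.8 v 73.2 | 73.9 v 73.6 | 75.6 v 73.3 | 81.0 v 74.5 |
| 30 v 43 (moderate) | 73.3 v 76.2 | 74.1 v 75.6 | 76.1 v 75.3 | 80.6 v 74.8 |
| 20 v 33 (strong) | 73.3 v 84.0 | 73.0 v 83.8 | 74.1 v 83.5 | 80.8 v 83.8 |

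Monte Carlo SE is about 0.4 points near 90% power and 0.6 near 75%.

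**Other results from the same simulation.**

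- Type I error: switch 4.9% to 5.7%, HC2 regression 4.9% to 5.4%.
- The switch goes to Wilcoxon in 18% to 20% of trials (40 v 56), 53% to 55% (30 v 46) and 99% (20 v 36). These rates depend on the assumed distribution and normality test.
- The two tests disagree at 0.05 in 2% to 6% of trials at 16 mm and 4% to 12% at 13 mm.
- For a true mean difference of 16 mm the Hodges-Lehmann shift averages 16.7 to 16.9 mm. Within a trial the two estimates differ by 0.9 to 1.4 mm on average (90th percentile 1.8 to 3.0 mm).

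**The case against.** The strongest reply is that little harm is shown. The comparison is randomized, the switch keeps type I error near 5%, and the two mm estimates usually agree within 2 to 3 mm. Even an analyst who took the smaller of the two p-values would reach only about 6% (5.9% and 6.2% in separate simulations with near-normal and skewed scores). An unadjusted comparison is legitimate, and many baseline scores may sit near zero and predict little. All of this stands, and it limits the weight of the point.

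The second reply is that the proposed regression can do worse than what it replaces. This also stands. With an uninformative baseline it loses 0.4 to 2.9 points to the switch under mild or moderate skew. Under strong skew it loses about 6 points at 16 mm and 11 at 13 mm, and it is still slightly behind at latent r = 0.5. That loss comes from comparing means instead of ranks, not from the covariate: against a Welch t-test, adjustment for an uninformative baseline costs about a point or less. In a smaller check of 1,000 runs per case, a rank-based baseline adjustment recovered nearly all of the loss (93% v 94% at 16 mm, 86% v 87% at 13 mm).

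These replies bear on which analysis to fix. They do not remove the need to fix one and to name its estimate.

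**Conclusion.** The point holds as a specification gap with a cheap improvement, at the level of something to consider. The plan leaves the test to the outcome data without a criterion, names no estimate or interval in mm, and does not use the baseline score. The possible gain in power at 16 mm runs from nothing at r = 0 to 6.6 points at r = 0.5 (95.9 − 89.3) under normal theory, given SD 20 mm, 33 per arm and a two-sided test. Because r is not given, this is a range and not an expected benefit.

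Three stronger readings are tempting, and the documents do not support them.

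- **That the switch makes the primary test invalid.** The simulated type I error does not show this.
- **That the primary outcome is undefined and might be change from baseline.** The Statistical analyses section says only pain, but the Introduction ties the aim to pain at placement, and nowhere is a change score proposed. The raw or change choice deserves one clarifying word. It is not evidence of a different outcome.
- **That leaving out baseline is an error that costs the trial its power.** It is a permissible choice whose cost is unknown.

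**What to change.** Replace the primary-outcome sentence with one fixed analysis: a linear regression of the raw VAS score at tenaculum placement on arm and pre-speculum baseline pain, with an HC2 standard error, reporting the adjusted mean difference in mm with its 95% CI. Report the Wilcoxon test with the Hodges-Lehmann shift and its CI as a prespecified sensitivity analysis, not as a switch.

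Add one line saying that baseline is marked on the same 100-mm VAS and before allocation is revealed. The common scoring sheet in the provider script suggests the same scale, but the baseline step does not name it. The Randomization section puts the reveal before the speculum without saying whether the baseline mark comes first. Do not adjust for the post-speculum score, which follows the reveal.

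If the authors expect most scores near zero, they should instead fix the rank test as primary, with a Hodges-Lehmann shift in mm and CI, before any outcome data are seen.

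The cost is one paragraph of plan wording and one line on the order of baseline mark and reveal. The Data collection section already stores the pain responses, so nothing new is collected. The price in power is the loss set out under the objection, which is largest if scores are strongly skewed toward zero.

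### The chi-square or Fisher test planned for the 1-to-5 provider satisfaction score ignores the order of the scale, so it does not test the hypothesis of higher satisfaction

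*Combined protocol and SAP*

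**What the plan says.** Three places bear on the point.

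- **Scale** (Procedure at time of IUD insertion). The provider's rating is defined by five labelled scores: "1: not at all satisfied, 2: slightly satisfied, 3: moderately satisfied, 4: very satisfied, 5: extremely satisfied". The five levels are ordered.
- **Role and hypothesis** (end of the Introduction). "Provider satisfaction with tenaculum placement will be measured as a secondary outcome". The hypothesis is that "slow tenaculum placement is less painful to patients and offers higher provider satisfaction scores".
- **Test** (Statistical analyses). The arms are compared on the "secondary outcome of provider satisfactions with placement using Chi-square test", with Fisher's test as the alternative. The sentence before it reads "We will compare groups on the primary outcome of pain using T-tests versus Wilcoxon test pending the normality of the results", so a rank test is already in the plan, but only for pain.

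For satisfaction the document gives no cut-point, trend version, rank test, ordinal model or effect estimate. The remaining analysis sentence concerns correlations with patient characteristics and physician experience, not the comparison of the arms.

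**The concern.** A chi-square or Fisher test on two arms by five levels asks whether the two patterns of ratings differ in any way. The hypothesis asks whether one arm tends to score higher. These questions can have different answers. The planned test can be significant when neither arm scores higher, and it can miss a consistent upward shift because its sensitivity is spread over 4 degrees of freedom. With 66 ratings, the p-value may not answer the stated secondary question, and a roughly uniform shift in satisfaction is less likely to be found.

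**Working it through.** **Inputs.** From the document: a five-level ordered scale, a directional hypothesis, a chi-square or Fisher test, and a total of 66 (Sample size determination). Assumed: 1:1 allocation, hence 33 ratings per arm, because the ratio is not stated; independent ratings; two-sided 0.05. The document gives no satisfaction distribution or effect size, so those are assumed and varied below.

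**The plan's own figure.** The 66 was set for pain, and no SD is stated. It is reproduced at an assumed SD of 20 mm: n per arm = 2 x (1.960 + 1.282)² x 20² / 16² = 32.8, rounded up to 33, total 66. Here it serves only as the number of ratings.

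**Step 1: order is ignored.** With equal arms the expected count in each cell is half the column total m, so chi-square = sum over levels of 2(a − m/2)² / (m/2), where a is the count in one arm. The terms are simply added, so their order cannot matter.

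**Step 2: a steady upward shift.** Constructed counts for scores 1 to 5: cough 5/8/10/6/4 (mean 95/33 = 2.88), slow 2/4/9/9/9 (mean 118/33 = 3.58).

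- Column totals are 7/12/19/15/13. Chi-square = 1.286 + 1.333 + 0.053 + 0.600 + 1.923 = 5.19 on 4 df, p = 0.268. All 120 orderings of the columns give the same p. Fisher p = 0.28.
- Midranks are 4, 13.5, 29, 46 and 60. The slow-arm rank sum is 1277 against an expected 33 x 67/2 = 1105.5. The tie-corrected variance is (33 x 33/12) x [67 − 14436/(66 x 65)] = 5775, so z = 171.5/76.0 = 2.26 and p = 0.024.
- The probability that a slow rating exceeds a cough rating, ties counted half, is (1277 − 561)/1089 = 0.657. The common odds ratio is 2.80 (95% CI 1.15 to 6.82).

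**Step 3: no difference in level.** Constructed counts 0/8/17/8/0 and 8/4/9/4/8 both have mean 3.0. Chi-square = 8 + 1.333 + 2.462 + 1.333 + 8 = 21.13 on 4 df, p = 0.0003. Rank-sum p = 1.0.

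**Step 4: power.** Shift model: logit P(score ≤ k, slow) = logit P(score ≤ k, cough) − log OR. There were 20,000 simulated trials per cell. Reference distributions: A (.10, .20, .40, .20, .10); B (.05, .10, .20, .35, .30); C uniform. Entries are Wilcoxon v chi-square power, in percent.

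| OR | A | B | C | Chi-square loss (points) |
|---|---|---|---|---|
| 1.5 | 14.4 v 8.5 | 14.4 v 8.0 | 14.7 v 9.0 | 5.7–6.4 |
| 2 | 33.1 v 18.1 | 32.9 v 17.1 | 34.2 v 19.3 | 14.9–15.8 |
| 2.5 | 52.3 v 30.5 | 51.4 v 29.8 | 53.3 v 32.9 | 20.4–21.8 |
| 3 | 67.4 v 42.8 | 65.2 v 41.1 | 69.1 v 46.2 | 22.9–24.6 |
| 4 | 86.0 v 65.7 | 83.1 v 61.5 | 86.6 v 67.2 | 19.4–21.6 |
| 5 | 94.1 v 79.9 | 92.1 v 75.9 | 94.3 v 81.0 | 13.3–16.2 |
| 8 | 99.4 v 96.1 | 98.9 v 93.5 | 99.5 v 95.9 | 3.3–5.4 |

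Fisher's test (4,000 runs) is 12 to 23 points below Wilcoxon at odds ratios 2, 3 and 5. With no effect, Wilcoxon rejects in 4.4–5.0% of runs and chi-square in 3.9–4.8%, so both hold the type I error.

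**Step 5: ratings near the ceiling.** With reference (.001, .009, .04, .30, .65) the chi-square loss is 4.7 to 14.4 points over odds ratios 1.5 to 8. In a near-complete ceiling (about 0, .001, .02, .30, .679) it is 2.5 to 6.9 points.

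**The case against.** **The plan does not say that all five levels are kept.** If the score were cut into two groups, a 2 x 2 test would compare levels of satisfaction. Cutting the Step 2 table at 4–5 v 1–3 gives 18/33 v 10/33, uncorrected chi-square p = 0.046 (Fisher 0.080). At odds ratio 3 that cut has about 62%, 47% and 63% power for distributions A, B and C, a loss of roughly 6 to 19 points against Wilcoxon rather than 23 to 25. But no cut-point appears anywhere, and one chosen after seeing the data would be worse. Five levels is the natural reading.

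**The planned test is valid, and the counts would show direction.** This is true and limits the harm. The plan still provides no test or interval for that direction.

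**Wilcoxon is favoured by the proportional-odds model and does not always win.** This also stands. With the Step 3 distributions as the truth, Wilcoxon rejects in about 6% of trials and chi-square in more than 99%. For shifts confined to two adjacent categories, (.05, .10, .20, .60, .05) v (.05, .10, .20, .25, .40) gives about 40% v 91%, and (.05, .10, .50, .05, .30) v (.05, .10, .20, .35, .30) gives about 23% v 84%. Spread-only differences are not what the hypothesis is about. The adjacent-category cases are a real cost of the change.

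**Ratings may cluster by provider.** This was not modelled. It would affect the planned test and its replacement alike.

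**Conclusion.** The concern holds. The scale is ordered, the hypothesis concerns higher scores, and the only planned comparison of the arms disregards order. That mismatch needs no assumption beyond reading the table as 2 x 5. Its size in power does rest on assumption: 13 to 25 points for chi-square at odds ratios 2 to 5 under proportional odds, 33 per arm and distributions A to C; about 6 points at 1.5 and 3 to 5 at 8; less near a ceiling; and a reversal for the irregular patterns described above. This is a secondary outcome. Type I error, the primary pain analysis and the total of 66 are untouched. The plan should be changed on this point, but the trial does not depend on it.

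**What to change.** Replace the satisfaction sentence in Statistical analyses with, for example: *Provider satisfaction (1–5) will be compared between arms with a two-sided, tie-corrected Wilcoxon rank-sum test. The common odds ratio from a proportional-odds model and the probability that a slow-arm rating exceeds a cough-arm rating (ties counted half), each with a 95% CI, will be reported next to the 2 x 5 table of counts by arm.*

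Reporting both estimates whatever the fit avoids a data-driven choice between them; the second does not depend on proportional odds. The directional hypothesis does not call for a one-sided test.

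The cost is a short SAP edit, with no new data and no change to the sample size. The downside is lower power if the arms differ only in spread or in two adjacent categories; the reported counts keep such patterns visible.
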